5.7 Patient Withdrawal

A patient should be removed from the study whenever it is necessary to safeguard his/her welfare. Occurrence of a significant adverse event or laboratory abnormalities unexpected for these patients may also necessitate discontinuation from the study. Additional reasons for removing a patient from the study are:

- Patients who participate in another investigational drug trial
- Patients' non-compliance with the protocol that can negatively affect the treatment effect
- Patients who express a desire to withdraw from the study (the patient has the right to withdraw for any reason without prejudice)
- Evidence of progressive disease would require withdrawal of the patient from the study.
- Any other reasons deemed by the principal investigator and treating physician.
- Patients who must discontinue use of either CT-011 or lenalidomide

The reason for any patient withdrawal from the study should be recorded on the case report form (CRF) and the occurrence should be reported to the principal investigator by email. These patients who withdraw from the study in the phase II portion of the trial will not be replaced. When a patient is removed from the study, he/she will receive treatment according to the standard of care (SOC) in the medical center and will be followed-up according to the study schedule whenever possible.

A patient who is removed from the study by the investigator due to an adverse event (AE) or serious adverse event (SAE) will be followed until resolution of the toxicity to Grade 1 or baseline. All the tests that are required to assess the patient condition will be made as frequent as necessary until the AE or SAE has been resolved. Samples that have already been obtained will be processed.

A patient who withdraws consent before starting the study will not be followed up.

A patient who is removed from the study by the investigator since he/she did not keep the appointments will be hard to follow given the circumstances. The extreme situation of this occurrence is a patient who is defined as "lost to follow-up". Attempts to follow up on the subject will be made as long as the consent has not been withdrawn by the subject. Samples that have already been obtained will be processed.

A patient who initiated another treatment not allowed in the protocol is to be removed from the study by the investigator. Follow up will be only for safety per above. Attempts to continue the follow up of the patient by monthly phone calls or other means will be made to collect information on the patient's survival. Samples that have already been obtained will be processed.

5.8 Schedule of Tests and Observations

5.8.1 Screening

Medical history & clinical examination, ECOG/WHO PS, vital signs, concomitant medications, date of diagnosis, previous treatment, and appropriate assessment of inclusion and exclusion criteria will be performed within 4 weeks prior to starting protocol-based therapy.

5.8.2 Evaluation during treatment

Clinical examination, ECOG/WHO PS, vital signs, toxicity assessment and documentation of concomitant medications will be performed at each outpatient visit. Toxicity will be assessed according to the NCI CTCAE

5.8.3 Post-treatment Follow-up

After the end of study treatment (whatever the reason for discontinuation), the patient will be followed for 6 months. Adverse events will be followed for at least 30 days, during which time all procedures for the reporting of SAEs will be followed.

- a. All patients who discontinue the trial secondary to an adverse event thought to be related to protocol therapy (probably, possible, or definite) should be followed until resolution, stabilization, return to a baseline condition, or death. Overall and progression free survival will be determined through clinic visits or phone interviews with clinical research staff. Follow up data should be submitted at 1 month after protocol therapy discontinuation and then every 3 months until progression or death, whichever occurs first.

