4.4 Duration of Treatment

Patient can continue study treatment at the treating physician's discretion. Patients achieving at least a stable disease can continue treatment until one of the following is reached:

- Progression of disease
- Death
- Unacceptable toxicity
- Patient decision
- Treatment delay greater than 4 weeks.

Overall response will be assessed after 4, 8, and 12 cycles. If disease progression is observed at the end of Cycle 4 evaluation, all study therapy will be discontinued. In addition, study therapy will be discontinued at the time of disease progression as noted above. Otherwise patient can continue treatment until one of the above endpoints is reached.

Following the 30-day post-treatment follow-up assessment, additional evaluations will occur once per month (unless subject discontinued due to progression) until the earliest of the following events:

- Disease progression,
- The time of initiation of new therapy,
- Death or study completion.

Study completion is defined as 30 days after the last subject remaining on study medication discontinues study medication.

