5.8.6 Schedule of Events^a

Investigations	Screening	C1D3	C1D4	C1D6	C1D10	C1D17	C2D3	C3D3	C5D3	CxD3	End of Tx ^b	Follow Up ^p
History, physical examination, concomitant medication review	X	X					X	X		X	X	
Informed written consent	X											
Confirmation of disease relapse and prior treatment	X											
Skeletal survey (CT or MRI as clinically indicated) ^c	X										X	
MUGA or ECHO	X											
β-hCG ^d	X	X										
Toxicity evaluation	X	X					X	X		X	X	X
CBC / differential / platelets ^e	X	X					X	X	X	X ^f	X	
PTT, INR, TSH ^e	X											
BMP, glucose, magnesium ^e	X	X					X	X		X		
LFTs	X	X					X	X		X		
Beta 2 microglobulin ^g	X							X			X	
12-lead ECG ^h	X							X				
Serum monoclonal protein assessments ⁱ	X	X ⁱ					X ⁱ	X ⁱ		X ⁱ	X ⁱ	
24hr urine for creatinine clearance	X											
24hr urine monoclonal protein and immunofixation ^j	X	X ^j					X ^j	X ^j		X ^j	X ^j	
BM biopsy, unilateral ^k	X								X ^k		X ^k	
CT-011 Given		X					X	X	X	X		
Prescribe lenalidomide via RevAssist ^l	X											
T-cell, NK-cell, and CD14 Correlative studies ^m	X	X	X	X	X	X	X	X	X	X	X	X

CT-011 PK ⁿ		X	X	X	X	X	X				
ADA (immunogenicity) ^o	X										

- a. With the exception of PK samples, all other time points have a +/- 4 day window to accommodate weekends, holidays, and for patient convenience.
- b. Off study correlates will be done. In addition, continued T-cell correlate will be done at 1,3, and 6 months after removal from study
- c. Skeletal survey will be done at baseline and may be done at evidence of progression of disease. CT scan will be done to document size of plasmacytoma if this is the only measurable disease.
- d. Female patients of childbearing potential (FCBP, defined in section 8.5) must have a negative pregnancy test (β -hCG) as required by the RevAssist program. Lenalidomide and dexamethasone will start on day 1 of each cycle. Patients do not need to be in clinic to initiate this as all patients would have been exposed to both. Lenalidomide will be ordered for the next cycle. A pregnancy test (urine or serum β -HCG) will also be ordered at this time. Patients must have a negative β -HCG result prior to starting lenalidomide on day 1 of each cycle.

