- **Inconclusive**: The results of this study will be classified as inconclusive with respect to this regimen demonstrating an improved response rate if only 10 or 11 of the 29 total evaluable patients have a response after 4 cycles of therapy. In this case, other factors such as progression-free survival, toxicity, and correlative outcomes will be used in addition to the response data to make the final determination as to whether or not this treatment is considered promising and worthy of further study in this patient population.

In this type of three-outcome phase II design with an uncertainty region, the associated errors are not the same as in the standard phase II study designs. In this study, the type I and type II error rates are constrained at 4% and 3%, respectively; The other parameters included in this type of design are eta (the probability of determining that a regimen is not worth pursuing further when it truly is not effective) and pi (the probability of determining that a regimen is promising when it truly is). Under this design, eta=0.83 and pi=0.87.

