6.3 Clinical outcome definitions

Time to progression: TTP will be defined as the time from start of treatment until the date he or she has progression or dies. Any subject who has received study treatment but has neither progressed nor died will be censored on the date of his or her last tumor assessment. A subject who has not received study treatment and who has neither progressed nor died will be censored on the day he or she was enrolled.

Progression Free Survival: PFS will be defined as the time from study entry until disease progression or death at trial closure for the per protocol population. Patients who withdraw from the trial prior to disease progression and who are either lost to follow-up, die or who begin alternative treatments prior to progression, will have their data censored as of the date considered to be lost to follow-up, date of death, or the first day of alternative therapy.

Time to Response: A subject's time to response is defined as the time from first dose of study therapy until measurement criteria are first met for [VG]PR or CR or SD (whichever status is recorded first). Time to response is computed only for subjects whose best response is [VG]PR or CR.

Duration of Overall Response: The duration of overall response will be computed for subjects whose best response is either [VG]PR or CR or SD. It will be measured from the time measurement criteria are first met for complete response or partial response (whichever status is recorded first) until the first date of progressive disease or death. Subjects who neither progress nor die will be censored on the date of their last tumor assessment.

Overall Survival: A subject's survival time will be defined as the time from start of treatment to the date of his or her death. If the subject has not died, survival will be censored on last date the subject was known to be alive.

Response Rate: The tumor response rate will be defined as the total number of subjects whose best response is PR or VGPR or CR or SD, divided by the number of per protocol patients.

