Appendix B: IMWG Response Criteria

Serum and urine M-protein estimates will be performed every 4 weeks; except for assessment of CR, patients with measurable disease restricted to the SPEP (or UPEP) will need to be followed only by SPEP (or UPEP). Responses will be assessed according to the criteria of the International Myeloma Working Group⁶¹, and characterized as follows:

Response Category	Response Criteria ^a
SCR	CR as defined below plus 
 • Normal FLC ration and • Absence of clonal cells in bone marrow^b by immunohistochemistry or immunofluorescence^c
CR	Negative immunofixation on the serum and urine and disappearance of any soft tissue plasmacytomas and $\leq 5\%$ plasma cells in bone marrow ^b
VGPR	Serum and urine M-protein detectable by immunofixation but not on electrophoresis or 90% or greater reduction in serum M-protein plus urine M-protein level < 100 mg per 24 hours
PR	$\geq 50\%$ reduction of serum M-Protein and reduction in 24 hour urinary M-protein by $\geq 90\%$ or to < 200 mg per 24 hours If the serum and urine M-protein are unmeasurable ^d a $\geq 50\%$ decrease in the difference between involved and uninvolved FLC levels is required in place of the M-protein criteria If serum and urine M-protein are unmeasurable, and the serum free light assay is also unmeasurable, $\geq 50\%$ reduction in plasma cells is required in place of M-protein provided baseline bone marrow plasma cell percentage was $\geq 30\%$ In addition to the above, if present at baseline a $\geq 50\%$ reduction in the size of soft tissue plasmacytomas is also required
SD^e	Not meeting criteria for CR, VGPR, PR, or progressive disease
Relapse Category^f	Relapse Criteria
Progressive disease	Requires only one of the following: Increase of $\geq 25\%$ from baseline in: 
 • Serum M-component and/or (the absolute increase must be ≥ 0.5 g/dl)^g • Urine M-component and/or (the absolute increase must be ≥ 200 mg/24 hours) • In patients without measurable serum and urine M-protein levels the difference between involved and

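### The documents conflict on disease follow-up for patients who stop treatment without progression, and the schedule table contains no M-protein test by which a later progression could be established.

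*Combined protocol and SAP*

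**What the plan says.** Four parts of the protocol govern the period after treatment.

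- **Section 5.8.3** opens with "After the end of study treatment (whatever the reason for discontinuation), the patient will be followed for 6 months". It then says "Overall and progression free survival will be determined through clinic visits or phone interviews with clinical research staff", and "Follow up data should be submitted at 1 month after protocol therapy discontinuation and then every 3 months until progression or death, whichever occurs first". Footnote p of the schedule repeats the last two statements but not the 6-month period.
- **Section 4.4** (and the synopsis) says that after the 30-day visit "additional evaluations will occur once per month (unless subject discontinued due to progression"), up to progression, new therapy, death or study completion. It does not say what an evaluation contains.
- **Section 5.8.6** has a row "Serum monoclonal protein assessments" marked at screening, on treatment and at End of Tx, with nothing under Follow Up. Only toxicity evaluation and correlative studies are marked there. Footnote i ends serum testing at the off-study visit; footnote j ties urine testing to screening and response assessment.
- **Appendix B** says "Serum and urine M-protein estimates will be performed every 4 weeks" and gives no end at treatment stop. Its footnote f requires two consecutive assessments before progression is declared.

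Section 6.3 sets the censoring. For TTP, a treated patient who has "neither progressed nor died will be censored on the date of his or her last tumor assessment"; death is an event. Response duration uses the same censoring date. PFS is worded differently: a withdrawn patient is censored at loss to follow-up, death or the first day of alternative therapy. Section 6.1.2 adds that, when 10 or 11 of 29 patients respond, "other factors such as progression-free survival, toxicity, and correlative outcomes will be used" alongside the response data.

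**The concern.** Patients can leave treatment without progression by several routes: toxicity, a delay of more than 4 weeks, having to stop either drug, or their own choice (4.4, 5.7). For them, progression is found only if someone measures the disease after treatment. Appendix B progression rests on M-protein, FLC, marrow, imaging or calcium, and a phone interview supplies none of these. Section 5.7 directs that removed patients be followed according to the study schedule where possible, and the schedule table has no disease assessment after End of Tx. A site working from the table would order nothing; a site working from 4.4 and Appendix B would test about monthly.

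Whether and when a progression is recorded could therefore depend on which page a site follows. At stake are TTP (a secondary endpoint in 2.4), response duration, and PFS as one of the deciding factors in the inconclusive zone.

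**Working it through.** **1. The design figures and the zone where PFS matters.** Inputs from 6.1.2: n = 29, response rates 25% and 50%, cut-offs ≤9, 10–11 and ≥12. With X binomial:

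- type I error = P(X ≥ 12 | 0.25) = 0.039 (stated 4%)
- type II error = P(X ≤ 9 | 0.50) = 0.031 (stated 3%)
- eta = P(X ≤ 9 | 0.25) = 0.834 (stated 0.83)
- pi = P(X ≥ 12 | 0.50) = 0.868 (stated 0.87)

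The plan's figures reproduce. The inconclusive zone is the remainder: 1 − 0.834 − 0.039 = 0.127 at 25%, and 1 − 0.868 − 0.031 = 0.102 (unrounded terms) at 50%. At a true rate of 35%, between the two design rates, P(X = 10 or 11) = 0.154 + 0.143 = 0.297.

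**2. The follow-up rules side by side**

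| Source | Duration | Interval | Disease test named |
|---|---|---|---|
| 5.8.3, first sentence | 6 months | none | none |
| 5.8.3 and footnote p | to progression or death | data at 1 month, then every 3 months | none; visit or phone |
| 4.4 | to progression, new therapy, death or study completion | monthly | none |
| Appendix B | not limited | 4 weeks | serum and urine M-protein |
| 5.8.6, Follow Up column | – | – | none |

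The 6-month limit cannot be squared with the open-ended rules, and the last two rows conflict on whether M-protein is measured at all. If the table governs, the last tumor assessment is the End of Tx one, which fixes the censoring date for TTP and response duration. PFS has no such rule, so the same patient can run on as progression-free, untested, until lost or started on another therapy.

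**3. Illustrative size for TTP.** The documents give no rate of stopping without progression, so these inputs are assumptions: exponential progression with on-treatment median 7.7 months (the once-daily median PFS in 1.3.1), hence λ = ln 2 / 7.7 = 0.0900 per month; 30% of patients assigned a stop time u, uniform on months 1 to 6; hazard after stopping kλ.

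True survival for t > 6 and k ≠ 1:

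S(t) = 0.7·e^(−λt) + 0.3·e^(−kλt)·[e^(6(k−1)λ) − e^((k−1)λ)] / [5(k−1)λ]

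For k = 2 at t = 6.82: 0.7 × 0.541 + 0.3 × 0.293 × 1.382 = 0.379 + 0.121 = 0.500, so the true median is 6.82. Because u is independent of on-treatment progression, Kaplan-Meier with censoring at the stop returns 7.7 whatever k is.

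| k | True median (months) | Censored at stop | Overstatement |
|---|---|---|---|
| 1 | 7.70 | 7.70 | 0 |
| 1.5 | 7.18 | 7.70 | 0.5 |
| 2 | 6.82 | 7.70 | 0.9 |
| 3 | 6.35 | 7.70 | about 1.3 |

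Share censored at stop: 0.3 × (e^(−λ) − e^(−6λ)) / (5λ) = 0.3 × (0.914 − 0.583)/0.450 = 0.22, or about 6 of 29.

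**4. A second set of assumptions.** Let stopping be exponential, with 20% to 40% stopping by month 12 in the absence of progression, and take k = 2. Simulation gives true medians of 7.3 to 6.9 months against a reported 7.7. With an on-treatment median of 11.1 (a TTP in Table 1-1), it gives 10.3 to 9.6 against 11.1. The direction is the same and the size similar.

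**The case against.** The strongest reply is that the documents are inconsistent rather than silent. Monthly evaluations until progression presuppose something capable of detecting it, and Appendix B's 4-weekly M-protein has no stop at the end of treatment. On that reading, patients continue to be tested and the table merely omits a row. This stands: a reader might infer that the plan censors patients when they stop treatment, but no rule says so. That outcome follows for TTP and response duration only if the table governs. It does not describe PFS, and deaths after stopping remain TTP events.

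A reader might also take the 3-monthly text as a competing assessment timetable. It is worded as a data-submission interval and can coexist with monthly evaluations. Likewise, the visit-or-phone sentence covers overall survival, for which a phone call is adequate.

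On size, neither the stopping share nor the hazard rise comes from the documents; with no hazard rise, events are lost but the median is not biased. Sampling error is also larger: with an assumed 22 events, 7.7 × e^(±1.96/√22) gives about 5 to 12 months. Section 6.1.2 calls the PFS and OS analyses exploratory, and no power or comparator is set for TTP or PFS.

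These points limit the consequence. They do not remove the conflict: 5.7 points sites to the schedule, and the schedule has no disease assessment in this period.

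**Conclusion.** The point holds as a conflict between passages that must be reconciled. Disease follow-up after a stop without progression has incompatible durations, and the documents disagree on whether M-protein is measured. If the schedule table is followed, later progressions cannot be established under Appendix B; TTP and response duration end at about the End of Tx assessment, and PFS may be extended without evidence.

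The primary ORR after 4 cycles and the 29-patient design are untouched. The effect is on a secondary endpoint, on response duration, and on PFS as one factor in a zone reached with probability 10% to 13% at the design rates. The overstatement of median TTP, 0 to about 1.3 months, is illustrative and depends on the assumed 30% stopping share and a post-stop hazard ratio of 1 to 3. The documents do not support saying that the trial's TTP will be biased by a given amount. The change is worth making because it is cheap, but the trial's main conclusion does not depend on it.

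**What to change.** Reconcile 4.4, 5.8.3, 5.8.6 (with footnotes i, j and p) and Appendix B as follows.

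1. State one timetable for progression follow-up in identical words in each place, for example the monthly evaluations already in 4.4, which fit Appendix B's 4 weeks.
2. For patients off treatment without progression, mark in the Follow Up column the M-protein or FLC test(s) by which that patient's disease is measurable, as Appendix B allows, until progression or new therapy. Accept local results.
3. Limit phone contact to survival and new-therapy status.
4. State that the 1-month and 3-monthly interval is for data submission, and remove the 6-month limit as it applies to progression.
5. In 6.3, align TTP and PFS censoring to the last adequate disease assessment.

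The cost is a schedule and wording amendment, plus some routine tests or retrieval of local results for patients off treatment without progression. The T-cell draws already planned at 1, 3 and 6 months cover part of this, but not monthly testing.

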5.8.4 Sample collection for immunologic correlative studies

All patients enrolled on this trial will have samples procured for all proposed laboratory correlative studies as summarized below. With each cycle, approximately 30-mL of blood will be collected and sent to [name]'s lab for processing. Upon receipt, each sample will be recorded and coded with a unique sample number to keep patient identification confidential. PBMCs and plasma (and/or serum) will be aliquoted and cryopreserved. The vials of viably frozen cells for all time points for each patient will be thawed at the same time whenever possible to avoid inter-experimental variability.

5.8.5 Schedule for correlative studies

Laboratory correlative studies will be obtained at screening, days 3, 4, 6, 10 and 17 of cycle 1, days 3 of subsequent cycles and off study. Off-study correlates should be obtained at the time the patient is removed from protocol for any reason. In addition, continued T-cell correlate will be done at 1,3, and 6 months after removal from study. Specimens obtained include BM aspirate (10-15 ml in green-top tubes using heparinized syringe) and peripheral blood (Three-10 ml green top tubes, 2 for cells and 1 for plasma).

5.8.6 Schedule of Events^a

Investigations	Screening	C1D3	C1D4	C1D6	C1D10	C1D17	C2D3	C3D3	C5D3	CxD3	End of Tx ^b	Follow Up ^p
History, physical examination, concomitant medication review	X	X					X	X		X	X	
Informed written consent	X											
Confirmation of disease relapse and prior treatment	X											
Skeletal survey (CT or MRI as clinically indicated) ^c	X										X	
MUGA or ECHO	X											
β-hCG ^d	X	X										
Toxicity evaluation	X	X					X	X		X	X	X
CBC / differential / platelets ^e	X	X					X	X	X	X ^f	X	
PTT, INR, TSH ^e	X											
BMP, glucose, magnesium ^e	X	X					X	X		X		
LFTs	X	X					X	X		X		
Beta 2 microglobulin ^g	X							X			X	
12-lead ECG ^h	X							X				
Serum monoclonal protein assessments ⁱ	X	X ⁱ					X ⁱ	X ⁱ		X ⁱ	X ⁱ	
24hr urine for creatinine clearance	X											
24hr urine monoclonal protein and immunofixation ^j	X	X ^j					X ^j	X ^j		X ^j	X ^j	
BM biopsy, unilateral ^k	X								X ^k		X ^k	
CT-011 Given		X					X	X	X	X		
Prescribe lenalidomide via RevAssist ^l	X											
T-cell, NK-cell, and CD14 Correlative studies ^m	X	X	X	X	X	X	X	X	X	X	X	X

CT-011 PK ⁿ		X	X	X	X	X	X				
ADA (immunogenicity) ^o	X										

- a. With the exception of PK samples, all other time points have a +/- 4 day window to accommodate weekends, holidays, and for patient convenience.
- b. Off study correlates will be done. In addition, continued T-cell correlate will be done at 1,3, and 6 months after removal from study
- c. Skeletal survey will be done at baseline and may be done at evidence of progression of disease. CT scan will be done to document size of plasmacytoma if this is the only measurable disease.
- d. Female patients of childbearing potential (FCBP, defined in section 8.5) must have a negative pregnancy test (β -hCG) as required by the RevAssist program. Lenalidomide and dexamethasone will start on day 1 of each cycle. Patients do not need to be in clinic to initiate this as all patients would have been exposed to both. Lenalidomide will be ordered for the next cycle. A pregnancy test (urine or serum β -HCG) will also be ordered at this time. Patients must have a negative β -HCG result prior to starting lenalidomide on day 1 of each cycle.
- e. CBC d/p will be monitored biweekly in cycles 1 to 4, then monthly thereafter. Chemistry tests, including electrolytes, glucose and serum creatinine, should be performed every 2 weeks during the first 2 months of therapy and once a month thereafter. Serum electrolyte monitoring should include potassium, magnesium and calcium. PTT, INR and TSH will be checked every 2 months.
- f. CBC/d/p should also be checked on day 17 of a cycle where lenalidomide's dose has been escalated.
- g. Beta 2 microglobulin will be done after every 2 cycles and at evidence of progression of disease.
- h. Baseline and periodic ECGs should be performed during treatment as indicated in the flow chart. In patients who have ECG abnormalities, ECGs should be performed more routinely as clinically indicated. ECGs post-baseline should be performed as indicated
- i. Myeloma monoclonal protein assessments (Serum protein electrophoresis & immunofixation, immunoglobulin levels, serum free light chain assay) will be performed on day 3 of each cycle (when patients come in for CT-011 infusion) as well as off study.
- j. 24hr urine monoclonal protein assessment (Urine protein electrophoresis & immunofixation) will be performed at screening and as required for response assessment.
- k. Unilateral bone marrow (BM) biopsy will be done at baseline and at end of 4th cycle and evidence of progression for patients with non secretory multiple myeloma
- l. Lenalidomide must be prescribed through and in compliance with Celgene's RevAssist® program. Prescriptions must be filled within 7 days. Any unused lenalidomide should be returned to the patient for disposition in accordance with the RevAssist® program.
- m. T-cell, NK-cell, and CD14 correlates will be collected prior to CT-011 dosing on C1D3, C1D4, C1D6, C1D10, C1D17 and then on Day 3 of all subsequent cycles. T-cell correlates only will also be collected at 1, 3, and 6 months after discontinuation of protocol therapy.
- n. Samples for CT-011 PK determination will be collected in cycle 1 prior to CT-011 infusion, immediately at the end of the infusion, 1 hour after end of infusion, approximately 24(C1D4), 72(C1D6), 168 (C1D10) & 336 (C1D17) hrs – and just prior to next (cycle 2) infusion. Off-study correlates should be obtained at the time the patient is removed from protocol for any reason.
- o. We will assess for immunogenicity at baseline and monthly starting 1 month after dose level 3 (3 mg/kg) is started. This will be done within 30 minutes of CT-011 infusion. This will be done by Medivation Inc. (see Appendix G)
- p. Adverse events will be followed for at least 30 days, during which time all procedures for the reporting of SAEs will be followed. All patients who discontinue the trial secondary to an adverse event thought to be related to protocol therapy (probably, possible, or definite) should be followed until resolution, stabilization, return to a baseline condition, or death. Overall and progression free survival will be determined through clinic visits or phone interviews with clinical research staff. Follow up data should be submitted at 1 month after protocol therapy discontinuation and then every 3 months until progression or death, whichever occurs first.

